CLASI	Cutaneous Lupus Erythematosus Disease Area and Severity Index
C _{max}	Maximum concentration
СМН	Cochran-Mantel-Haenszel
CTCAE	Common Terminology Criteria for Adverse Events
C _{trough}	Trough concentration
CV	Coefficient of variation
DMC	Data monitoring committee
dsDNA	Double stranded DNA
ECG	Electrocardiogram
EOS	End of study
EOT	End of treatment
FACIT-F	Functional Assessment of Chronic Illness Therapy-Fatigue
FDA	US Food and Drug Administration
ICH	International Counsel for Harmonisation of Technical Requirements for Pharmaceuticals for Human Use
ICOS-L	Inducible T cell co-stimulator ligand
IE	Intercurrent event
Ig	Immunoglobulin
Lambda z	Terminal elimination rate constant
LDA	Low Disease Activity by SLEDAI-2k
LLDAS	Lupus Low Disease Activity State

LOCF	Last observation carried forward
LS	Least squares
max	Maximum
MedDRA	Medical Dictionary for Regulatory Activities
min	Minimum
mITT	Modified Intent-to-Treat
MMRM	Mixed effects models for repeated measures
NAb	Neutralizing antibody
PhGA	Physician's global assessment of disease activity
PK	Pharmacokinetics
PT	Preferred term
PtGA	Patient's global assessment of disease activity
Q2W	Every other week
SAE	Serious adverse event
SAP	Statistical analysis plan
SD	Standard deviation
SDI	SLICC/ACR Damage Index
SF-36	Short Form Health Survey-36
SLE	Systemic lupus erythematosus
SLEDAI-2K	SLE Disease Activity Index 2000
SLICC/ACR	Systemic Lupus International Collaborating Clinics/American College of Rheumatology
SOC	System organ class
SRI	SLE Responder Index
t _{1/2}	Elimination half-life
TEAE	Treatment-emergent adverse event
Tmax	Time to maximum concentration
ULN	Upper limit of normal
V_d	Volume of distribution

1. INTRODUCTION AND BACKGROUND

The purpose of this Statistical Analysis Plan (SAP) is to describe the procedures and the statistical methods that will be used to analyze and report efficacy and safety results for Protocol AIS-A03, version 4.0 dated 7 November 2022, a randomized, double-blind, placebo-controlled study of ALPN-101 (acazicolcept) in systemic lupus erythematosus (SLE).

The structure and content of this plan provides sufficient detail to meet the requirements identified by the Food and Drug Administration (FDA) and International Conference on Harmonization of Technical Requirements for Registration of Pharmaceuticals for Human Use (ICH): Guidance on Statistical Principles in Clinical Trials.

This plan is a supplement to the study protocol, which contains additional details on study design, study conduct, and other operational aspects of the study.

2. STUDY OBJECTIVES

2.1. Primary Study Objective

The primary objective of the study is to evaluate the safety and tolerability of ALPN-101 compared to placebo in subjects with chronic, moderate to severe active SLE.

2.2. Secondary Study Objectives

The secondary objectives of this study are:

- Evaluate the efficacy of ALPN-101 in subjects with active SLE
- Assess PK of ALPN-101 in subjects with active SLE
- Assess the incidence of anti-drug antibodies (ADA) against ALPN-101 in subjects with active SLE

3. STUDY ENDPOINTS

3.1. Efficacy Endpoints

Definitions for efficacy endpoints are provided in Section 6.

3.1.1. Primary Efficacy Endpoints

There are two primary efficacy endpoints being investigated for this study:

[figure not shown]
- Achievement of SLE responder index (SRI)-4 at Day 169, or
- Achievement of British Isles Lupus Assessment Group-based Composite Lupus Assessment (BICLA) response at Day 169

3.1.2. Secondary Efficacy Endpoints

Secondary efficacy endpoints are provided below:

- Annualized flare rate by British Isles Lupus Assessment Group (BILAG)-2004 flare index through Day 169 all flares
- Time-to-first flare by BILAG-2004 flare index
- Achievement of Lupus Low Disease Activity State (LLDAS) at Day 169
- Change from baseline in Systemic Lupus Erythematosus Disease Activity Index 2000 (SLEDAI-2K) total score at Day 169
- Cumulative prednisone-equivalent dose use (total area under the curve of daily prednisone-equivalent dose) through Day 169
- Achievement of ≥50% reduction in Cutaneous Lupus Erythematosus Disease Area and Severity Index (CLASI) activity score at Day 169 in the subgroup of subjects with baseline CLASI activity score ≥8

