7.4.2. Handling of Missing Data and Intercurrent Events (IE)

Intercurrent events in this study include the following:

- IE1: Premature discontinuation of study treatment
- IE2: Restricted/rescue medication use (criteria for restricted/rescue medication use is provided in Section 6.21)

The strategies to be used in the handling of intercurrent events and missing data for efficacy endpoints, when applicable, are provided below:

- Binary endpoints (primary and secondary efficacy endpoints):
 - IE1 and IE2: subject is considered a non-responder (composite strategy)
 - Missing data for Day 169: subject is considered a non-responder
- Continuous endpoints measured through time (SLEDAI-2K total score):
 - IE1 and IE2: data after IE1 and IE2 occurs will not be included in the analysis (hypothetical strategy)
 - Missing data caused by applying the intercurrent event handling described above and other missing data will be handled by the mixed effects models for repeated measures (MMRM) analysis
- Other efficacy endpoints:
 - Treatment policy strategy will be applied and all observed data during the treatment period will be used regardless of IE1 or IE2
 - Missing data for Day 169 for binary endpoints: subject is considered a non-responder for applicable endpoints

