7.6. Analysis of Secondary Efficacy Endpoints

Unless otherwise stated, the mITT population will be the basis for analyses of all efficacy endpoints. These data will be analyzed through Week 24 (Day 169) for subjects who complete treatment and through the last assessment recorded \leq 28 days after treatment discontinuation for subjects who discontinue treatment early.

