7.6.2. Analysis of Continuous Endpoints

MMRM will be used for the analysis of continuous longitudinal data. Terms in the model will include treatment group, baseline value of the analysis variable, stratification factors (concomitant oral immunosuppressive therapy use at enrollment and geographic region), analysis visit, and the interactions of treatment-by-visit and baseline value-by-visit as fixed effects. An unstructured covariance matrix will be used to model within-subject error. If the model fails to converge with an unstructured covariance matrix, a heterogeneous compound symmetric structure will be used. Kenward-Roger degrees of freedom, Type III sums of squares, and least squares (LS) mean values will be reported for each treatment group and for the difference between treatments. Standard errors and 95% CI for the estimated mean difference at each visit will be presented. Plots of LS mean values and 95% CIs by visit with separate lines for each treatment group will be provided for continuous secondary efficacy endpoints.

Annualized flare rates and cumulative prednisone-equivalent dose use will be analyzed using an analysis of variance model. Terms in the model include treatment group and stratification factors (concomitant oral immunosuppressive therapy use at enrollment and geographic region). Type III sums of squares, and least squares (LS) mean values will be reported for each treatment group and for the difference between treatments. Standard errors and 95% CI for the estimated mean difference will be presented.

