7.7. Estimands for the Primary and Secondary Endpoints

Estimand definitions for the primary and secondary efficacy endpoints are provided below:

Table 2: Estimand Attributes Corresponding to the Primary and Secondary Efficacy Endpoints

	Attributes of the Estimand						
Estimand	Treatment	Endpoint	Population	Handling of Intercurrent Events	Statistical Summary		
Primary	ALPN-101 vs. Placebo	Achievement of SRI-4 response at Day 169	Subjects with moderate to severe SLE	IE1 and IE2: subject is considered a non-responder (composite strategy) Missing data: subject is considered a non-responder	Difference in the proportion of subjects achieving SRI- 4 response		
Primary	ALPN-101 vs. Placebo	Achievement of BICLA response at Day 169	Subjects with moderate to severe SLE	IE1 and IE2: subject is considered a non-responder (composite strategy) Missing data: subject is considered a non-responder	Difference in the proportion of subjects achieving BICLA response		
Secondary	ALPN-101 vs. Placebo	Annualized flare rate by BILAG- 2004 flare index through Day 169 for all flares	Subjects with moderate to severe SLE	All observed data used (treatment policy strategy)	Difference in the LS means for annualized flare rate by BILAG-2004 flare index for all flares		
Secondary	ALPN-101 vs. Placebo	Time-to-first flare by BILAG- 2004 flare index	Subjects with moderate to severe SLE	All observed data used (treatment policy strategy)	Hazard ratio for time-to- first flare by BILAG-2004 flare index		
Secondary	ALPN-101 vs. Placebo	Achievement of LLDAS response at Day 169	Subjects with moderate to severe SLE	IE1 and IE2: subject is considered a non-responder (composite strategy) Missing data: subject is considered a non-responder	Difference in the proportion of subjects achieving LLDAS response		

	Attributes of the Estimand						
Estimand	Treatment	Endpoint	Population	Handling of Intercurrent Events	Statistical Summary		
Secondary	ALPN-101 vs. Placebo	Change from baseline in SLEDAI-2K total score at Day 169	Subjects with moderate to severe SLE	All observed data used (hypothetical strategy)	Difference in the LS means for change from baseline in SLEDAI- 2K total score		
Secondary	ALPN-101 vs. Placebo	Cumulative prednisone- equivalent dose use through Day 169	Subjects with moderate to severe SLE	All observed data used (treatment policy strategy)	Difference in the LS means for cumulative prednisone- equivalent dose use		

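### Cumulative prednisone dose through Day 169 has no visible adjustment for days observed, so unequal early withdrawal would favour whichever arm loses more follow-up

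*SAP*

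**What the plan says.** - **Endpoint.** SAP 3.1.2: "Cumulative prednisone-equivalent dose use (total area under the curve of daily prednisone-equivalent dose) through Day 169". This is a quantity in mg that grows with time, not a daily average.
- **Intercurrent events.** SAP 7.4.2, for the group of other efficacy endpoints: "Treatment policy strategy will be applied and all observed data during the treatment period will be used regardless of IE1 or IE2". Table 2 in SAP 7.7 assigns the same treatment policy strategy to this endpoint.
- **Missing data.** The only missing-data rule in that group is: "Missing data for Day 169 for binary endpoints: subject is considered a non-responder for applicable endpoints". It does not reach a continuous total. The readable part of SAP 13 covers partial dates, BILAG laboratory data and grades, adverse event attributes and part of an imputation scheme for binary response. It has nothing on steroid dose after follow-up ends.
- **Observation period.** SAP 7.6: "These data will be analyzed through Week 24 (Day 169) for subjects who complete treatment and through the last assessment recorded" at most "28 days after treatment discontinuation for subjects who discontinue treatment early".
- **Model.** SAP 7.6.2: "Annualized flare rates and cumulative prednisone-equivalent dose use will be analyzed using an analysis of variance model". The terms are treatment group and the two stratification factors. There is no term, offset or weight for days observed.
- **Contrast.** The annualised flare rate shares that paragraph and model, but SAP 6.10 divides it by each subject's own exposure time.

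**The concern.** A total dose can be low because little steroid was taken each day or because few days were counted, and the model cannot tell the two apart. Treatment policy tells the analyst to keep data after an intercurrent event. It cannot supply data after a subject has left the study, and Protocol 4.3.2 allows withdrawal at any time. A truncated total would then enter the model beside complete 169-day totals as if the two were comparable.

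At stake is a secondary comparison that would be read as steroid sparing. If one arm loses more follow-up, part of the difference reflects follow-up time and not dosing. The SAP handles this for the flare rate, so leaving the steroid total unadjusted looks like an oversight.

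**Working it through.** **Plan figure.** The documents give no design calculation for this endpoint. SAP Table 1 covers SRI-4 and BICLA only. Its 82% and 87% for a 25-point difference reproduce (82.2% and 86.9%) but do not bear on this point.

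**Inputs from the documents.** Treatment period through Day 169; enrolment stopped at 76, so about 38 per arm (SAP 4.1); baseline dose at most 20 mg/day (Protocol 5.1); discretionary taper only after Day 85 (Protocol 8.2.2.2); oral burst up to 40 mg/day, back to the Day 1 dose within 14 days (Protocol 8.2.2.3). Withdrawal rates and the dose distribution are not given and are assumed below.

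**Step 1: one subject.** Total = daily dose × days observed. At a constant 10 mg/day:
- completer: 10 × 169 = 1,690 mg
- last observed on Day 85: 10 × 85 = 850 mg (−50%)
- last observed on Day 57: 10 × 57 = 570 mg (−66%)

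Divided by days observed, all three give 10 mg/day.

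**Step 2: against a genuine reduction.** Take the fastest taper within the protocol's guidelines from 10 mg/day, with each step at the start of its 28-day window. The total is 10 × 85 + 7.5 × 28 + 5 × 56 = 850 + 210 + 280 = 1,340 mg, a saving of 350/1,690 = 20.7%. A subject with no reduction at all whose records end before Day 134 (1,340/10) scores lower than that.

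As an extreme case, a subject on 10 mg/day takes 40 mg on all 14 days from Day 43 and is last observed on Day 56. The total is 10 × 42 + 40 × 14 = 980 mg. That is below the stable completer's 1,690 mg, although the average was 980/56 = 17.5 mg/day.

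**Step 3: between arms.** Bias (arm with more withdrawals minus the other) ≈ −(difference in withdrawal) × (mean dose) × (mean days lost). Assume a mean of 7.75 mg/day and withdrawal spread evenly over Days 29–154. The mean last day is 91.5, so 77.5 days are lost on average.
- 10 points: 0.10 × 7.75 × 77.5 ≈ 60 mg
- 20 points: 0.20 × 7.75 × 77.5 ≈ 120 mg

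Null simulations at 38 per arm agree: about −60 mg at 10% against 20%, about −115 to −124 mg at 10% against 30%, and about −121 mg at 5% against 25%. At 10% in both arms the bias is about zero. Against a full mean total of 7.75 × 169 ≈ 1,310 mg, 60 to 125 mg is about 5% to 10%.

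**Step 4: against sampling error.** With an assumed dose SD of 6.1 mg/day, the standard error of the difference before withdrawals is 6.1 × 169 × √(2/38) ≈ 237 mg. Simulated values with withdrawals are about 225 to 230 mg. The bias is therefore 60/225 ≈ 0.27 to 125/225 ≈ 0.56 of a standard error. Simulated false-positive rates are 5.6% to 8.8% against a nominal 5%. The 237 mg ignores the stratification factors, one of which depends on steroid dose; adjusting for them could shrink it, so the ratio is approximate.

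**Step 5: testing the remedy.** With constant doses and uninformative withdrawal, the time-averaged dose is unbiased by construction. With equal tapering in both arms after Day 85, the time-average (× 169) carries a bias of about +11 to +27 mg, against −50 to −98 mg for the raw total.

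**The case against.** The strongest reply is that the derivation may exist where it cannot be read. SAP 3.1 refers to Section 6 for endpoint definitions. In the public text, 6.12, 6.13, 6.16, 6.19, 6.20 and 7.5.2 do not appear, and cumulative prednisone is the only secondary endpoint without a readable Section 6 entry. Steroid doses are captured as concomitant medications (Protocol 4.4.4), and nothing readable says how a record still open at withdrawal enters the area under the curve. Closing it at last contact and carrying it to Day 169 are both compatible with the text. This stands, and it limits confidence. It does not remove the point, because the readable definition, estimand and model contain no time adjustment.

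Second, Protocol 4.3.2 and 6.6.1 keep subjects who stop study drug on the visit schedule, so true study withdrawals may be few. That is fair, but the cut-off in SAP 7.6, if applied here, would shorten those subjects' totals too. It also sits badly with the treatment policy wording in SAP 7.4.2, and the two need reconciling.

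Third, disposition by arm (SAP 7.1) would show unequal withdrawal. It would show it without correcting the estimate.

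Finally, this is one secondary endpoint with no multiplicity control (SAP 11), in a trial whose primary objective is safety and which was not sized for formal efficacy testing (SAP 4.2). That bears on priority, not on whether the total is comparable across subjects.

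**Conclusion.** The point holds with moderate confidence. On the readable text, a steroid user with shorter follow-up gets a mechanically lower total; a subject on 0 mg is unaffected. Bias between arms additionally needs unequal withdrawal. Under the assumed 10- to 20-point differences and 0–20 mg/day mix it is about −60 to −125 mg, roughly 0.3 to 0.55 of a standard error of about 225 mg.

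A reader might infer more than the documents support:
- **That the endpoint will make ALPN-101 look steroid-sparing.** No withdrawal rates are given, and the direction follows whichever arm loses more subjects.
- **That the SAP states a raw total over whatever days were observed.** Truncation at withdrawal is inferred from several sections read together; no sentence says it.
- **That false positives are badly inflated.** A rate near 24% appears at 30% against 10% withdrawal only if doses are tightly clustered (mean 10, SD 3 mg/day). Baseline doses may run up to 20 mg/day, and one stratum holds subjects on 5 mg/day or less, or none (SAP 4.3), so a wider spread is more plausible.
- **That mean daily dose is free of bias.** Step 5 shows a smaller bias of opposite sign once tapering is allowed for.

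**What to change.** In SAP 3.1.2 and 7.6.2:
- Make the analysis variable the mean daily prednisone-equivalent dose: the area under the curve divided by days from first dose to the earlier of Day 169 or the last day with medication data. Multiply by 169 if a total is wanted for display.
- Report days observed by arm beside the result.
- Add a sensitivity analysis that multiply imputes daily dose from withdrawal to Day 169. The time-average assumes that unobserved dosing resembles observed dosing, which is not exact when tapering is allowed only after Day 85.
- State whether the SAP 7.6 cut-off applies to this endpoint, so that it agrees with the treatment policy strategy.

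If an unpublished subsection already gives the derivation, a cross-reference from 7.6.2 would settle the definition. The main change costs a few sentences and one derived variable. The sensitivity analysis adds some programming. No new data are needed.

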3.2. Safety Endpoints

The primary study objective of assessing safety and tolerability of ALPN-101 will be evaluated using the endpoints listed in below:

- Treatment-emergent adverse events (TEAEs), treatment-emergent adverse events of interest (AEIs; infusion-related reactions, oral mucocutaneous lesions, infections grade ≥3), and serious adverse events (SAEs)
- Abnormal laboratory test results and observed and change/shift from baseline in over time for:
 - Chemistry
 - Hematology
 - Coagulation
 - Urinalysis
- Abnormal vital signs results and observed and change/shift from baseline over time for:
 - Systolic and diastolic blood pressures (mmHg)
 - Heart rate (bpm)
 - Respiratory rate (bpm)
 - Body temperature (°C)
 - Weight (kg)
- Abnormal electrocardiogram (ECG) parameters and observed and change/shift from baseline over time for:
 - Heart rate (bpm)
 - QT interval (msec)

- PR interval (msec)
- ORS duration (msec)
- RR interval (msec)
- QTcB interval (msec)
- QTcF interval (msec)

3.3. Biomarker

Key biomarker endpoints are specified below. Biomarker variables will also be analyzed over time, as applicable:

- Observed and change/percent change from baseline by visit for clinical biomarkers of SLE:
 - C-reactive protein
 - Complements C3, C4, CH50
 - Immunoglobulins (Igs) IgM, IgG, IgA, IgE
 - Anti-double stranded DNA (dsDNA) antibodies
- Proportion of subjects who converted from abnormal laboratory test values at baseline to normal laboratory test results at Day 169 in:
 - C-reactive protein
 - Complements C3, C4, CH50
 - Immunoglobulins IgM, IgG, IgA, IgE
 - Anti-dsDNA antibodies

3.4. Pharmacokinetic Endpoints

To examine the pharmacokinetics (PK) of ALPN-101 in subjects with active SLE the following variables will be analyzed:

- ALPN-101 concentrations for each timepoint
- Main PK parameters:
 - Area under the concentration-time curve (AUC)
 - Maximum concentration (Cmax)
 - Trough concentration (Ctrough)

- Elimination half-life $(t_{1/2})$
- Additional PK parameters:
 - Time to maximum concentration (Tmax)
 - Clearance (CL)
 - Volume of distribution (V_d)
 - Terminal elimination rate constant (Lambda z)
 - Accumulation ratios

3.5. Immunogenicity Endpoints

The following variables will be used to assess the immunogenicity of ALPN-101 over time:

- Incidence of ADA positive
- Minimum and maximum titer values
- Incidence of neutralizing antibodies (NAb) positive

4. STUDY DESIGN

4.1. General Description

This is a Phase 2, multicenter, multinational, randomized, double-blind, placebo-controlled, parallel-group study to evaluate the safety, tolerability, efficacy, immunogenicity, PK at LPN-101 compared to placebo in adult subjects with chronic, moderate to severe active SLE. At least 130 subjects will be randomized in a 1:1 ratio to receive a weight-based dose of 3 mg/kg ALPN-101 administered by intravenous infusion via an infusion pump or matching placebo every other week (Q2W) for a total of 12 doses. An overview of the study design is provided in Appendix 15.1.

Randomization will be stratified based by SLE treatment at baseline and geographic region (Appendix 15.5). Subjects will be followed for 4 weeks after the End of Treatment (EOT) visit, 6 weeks after the last dose of study drug. Assessments of adverse events (AEs) and disease activity, and collection of blood and urine for safety laboratory values, biomarkers of disease activity, PK, ADA, and will be performed throughout the study. The Schedule of Assessments is provided in Appendix 15.2.

Each subject will participate for up to 34 weeks, including:

- Screening Period: Up to 42 days prior to first dose date. All subjects must complete all screening assessments and make them available to the team for verification of disease activity. Subjects who appear to meet eligibility criteria must undergo central review and verification of SLE disease activity prior to randomization.
- Treatment Period: Up to 24 weeks from first dose date. Subjects will receive 12 doses of study treatments Q2W. Safety, biologic activity, PK, ADA, will be conducted according to the Schedule of Assessments (Appendix 15.2).
- Follow-up Period: 4 weeks after EOT.

Dense PK will be collected in subjects who agree to participate. Additional PK samples will be collected from these subjects 4 hours following administration of the first dose of study drug, and on days 1, 3 and 7 following the first study drug administration.

Medications that are used for treatment of SLE at baseline should be maintained at stable doses through the Day 169 assessments, except for incidences of toxicity or for a protocol-defined short-term increase (burst and taper) of corticosteroid dose in response to increased disease activity or reduction in corticosteroids (taper) to reduce toxicity in the context of improvement in disease activity.

Subjects who prematurely discontinue treatment with study drug should have all procedures outlined in the EOT visit and an unscheduled ECG performed as soon as possible, and not later than the next scheduled visit. To minimize missing data for efficacy and safety assessments, subjects who prematurely discontinue treatment, and who do not withdraw from the study, should otherwise continue their regular study visit schedule without receiving study drug. In subjects who are unable to continue their regularly scheduled visits, a follow-up phone call should occur approximately 8 weeks (corresponding to 5X half-life) after the last dose of study drug to determine the status of any ongoing AEs/ SAEs or the occurrence of any new AEs/SAEs.

Subjects who withdraw from the study prematurely (i.e., prior to Day 197), the End of Study (EOS) evaluations should be completed, if possible, preferably within 2 weeks of study drug discontinuation. In addition, a follow-up phone call should occur approximately 8 weeks (corresponding to 5x half-life) after the last dose of study drug to determine the status of any ongoing AEs/SAEs or the occurrence of any new AEs/SAEs.

It should be noted that while N=130 subjects were expected to be randomized in this study, enrollment was stopped at N=76 subjects.

